8 REGULATORY CONSIDERATIONS

8.1 Quality Control

8.1.1 Monitoring

AstraZeneca has delegated study monitoring to Syneos Health. Before the first patient is enrolled into the study, a Syneos Health designee will meet with the physicians (and other site personnel involved with the study) to discuss the joint responsibilities with regards to protocol compliance. The roles and responsibilities of Syneos Health and AZ or its representatives will be covered. This will be documented in a study Primary Agreement between the designated parties and the Primary Investigators (site physician) for each site.

During the study, a Syneos Health designee or AZ can implement various activities to assure compliance with AZ standards of quality. These activities could include but are not limited to:

Contacts with the sites to:

- Provide information and support to the physicians and other site personnel
- Ensure recruitment is meeting expectations for all sites
- Ensure that site personnel follow the appropriate process to ensure the patient ICFs are signed and stored at the site
- Ensure that site personnel follow the appropriate process to ensure patient's ON TRAX study participant identifiers are captured in the ICFs, as well as the contact details as required for the study

Monitoring activities (remotely, and before on site visit, if required) for:

- Checking a sample of ICFs at each site
- Checking a sample of patient data entry at each site

If there are any issues noted with ICFs or patient data entry that reflect a potential non-optimal level of protocol compliance by the site personnel, specific measures will be adopted by Syneos Health or AZ to evaluate the situation, identify the issue, and implement specific action plans to correct the situation.

8.1.2 Training of Study Site Personnel

The site physician will ensure that appropriate training relevant to the study is given to site personnel, and that any new information relevant to the performance of this study is forwarded to the staff involved.

Representatives of the AZ's quality assurance unit/monitoring team, AZ's delegate, and competent regulatory authorities must be permitted to inspect all study-related documents and other materials at the site that support study data entry, including the Investigator Site File, the completed ICFs and the patients' medical records. Audits may be conducted at any time during or after the study to ensure the validity and integrity of the study data.

8.1.3 Storage and Retention

Following closure of the study, the site physician has the responsibility to ensure maintenance of all site study records (except for those required by local regulations to be maintained elsewhere), in a safe and secure location.

The records must be maintained to allow easy and timely retrieval, when needed (e.g., for AZ's or its representative's audit or regulatory inspection) and must be available for review in conjunction with assessment of the facility, supporting systems, and relevant site personnel.

Where permitted by local laws/regulations or institutional policy, some or all of these records can be maintained in a format other than hard copy (e.g., microfiche, scanned, electronic); however, caution needs to be exercised before such action is taken.

The site physician must ensure that all reproductions are legible and are a true and accurate copy of the original and meet accessibility and retrieval standards, including regenerating a hard copy, if required. Furthermore, the site physician must ensure there is an acceptable backup of these reproductions and that an acceptable quality control process exists for making these reproductions.

AstraZeneca or its representatives will inform the site physician of the period for retaining these records to comply with all applicable regulatory requirements. The minimum retention time will meet the strictest standard applicable to that site for the study with a minimum of 5 years, as dictated by any institutional requirements or local laws or regulations, AZ/delegate standards/procedures, and/or institutional requirements.

8.2 Protection of Human Patients

This study will be performed in accordance with ethical principles that are consistent with the Declaration of Helsinki, Good Pharmacoepidemiology Practices (GPP), and applicable legislation for prospective studies.

The site physicians will perform data collection for the study in accordance with the regulations and guidelines governing medical practice and ethics in the United States.

The final protocol of the study, including the final version of the ICF, and submission of an Investigational Device Exemption must be approved or given a favorable opinion in writing by the appropriate Institutional Review Board (IRB) for each site.

The IRB must also approve amendments to the protocol and all advertising used to recruit patients for the study, according to local regulations.

8.2.1 Patient Informed Consent

The physician at each site will ensure that the patient is given full and adequate oral and written information about the nature, purpose, possible risk, and benefit of the study via the Informed Consent Process. Patients must also be notified that their participation is voluntary and they are free to discontinue from the study at any time. The patients should be given the opportunity to ask questions and allowed time to consider the information provided. The patients will be required to sign a statement of informed consent that meets the requirements of US FDA Code of Federal Regulations (CFR) 21CFR 50, local regulations, Health

Insurance Portability and Accountability Act (HIPAA) requirements, where applicable, and the IRB or study site.

Patients will be asked to contact the study site for issues related to study procedures or technical support. The study site will facilitate connection with the Current Health Call Center for assistance, as necessary. For medical questions or to report AE signs/symptoms, patients will be asked to contact their treating physicians directly.

It will be clearly explained to the patient that the study aims to collect data using certain devices, but that the use of these devices will not involve any additional risk for the patient. Patients will also be required to complete QoL and CCI [REDACTED] pertaining to the devices. The frequency of those measurements, the methods to guarantee no personal data are disclosed, and the right of the patient to access his/her information at any time during the study will all be communicated to the patient in a clear and unambiguous way.

The signed and dated patient ICF must be obtained before device onboarding for the study is performed.

The physician or designated site personnel must store the original, signed ICF. A copy of the signed ICF must be given to the patient at the time of consent.

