2.3 Benefit/Risk Assessment

All patients who participate in this study will receive standard of care appropriate for their lung cancer as determined by their treating physician.

The technology to be used in this study is non-invasive and has been used previously in other settings, including clinical studies; it is believed to pose an extremely low risk to study patients. Patients using the wearable arm device have reported minor events of skin irritation and discomfort during sleeping. In addition, patients undergoing concomitant anti-coagulation therapy have experienced ecchymosis near the device site. As part of their standard of care, patients will undergo routine assessment by their physician, who will decide when regular visits should take place. Due to the nature of the technology used and the fact that all other procedures are standard of care, study-related or multiparametric mobile technology-related AEs are expected to be rare. The study sponsor, AstraZeneca (AZ), has concluded that this study has a favorable benefit/risk ratio.

Data from this pilot study will be used by AZ to decide whether a larger comparative study of patients with and without the technology is warranted, which will potentially benefit other patients in the future.

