7.3 Data Collection Plan

The data collection plan presented in [Table 1](#) outlines all data points that will be obtained from patients' medical records, mobile devices, and QoL questionnaires, as collected in the tablet application, in the study. All patients in the study will attend routine visits, as recommended by the treating physician.

Table 1 Data Collection Plan for All Patients

Variables	Baseline (Day 1)	Daily Data Collection via Current Wearable Health Monitoring System	Data Collection via a Tablet Every 2 Weeks for First 3 Months and Once Monthly Thereafter	Standard of Care Visits	End-of-Study Visit	Safety Follow-Up (End-of-Study Visit +30 days)
Demographics: Age, gender; height	x					
Weight	x			x	x	
Blood pressure	x			x	x	
Vital Signs (temperature, heart rate, respiratory rate)	x	x		x	x	
NSCLC treatment and disease history, including time of most recent radiation	x					
Relevant medical and surgical history	x					
Pulmonary-related concomitant medication and procedures ^a	x			x	x	
All AEs/SAEs (including durvalumab-related and device-related AEs) ^b	x			x	x	x
If pneumonia or pneumonitis is diagnosed, details on pneumonitis and radiation pneumonitis if applicable	x			x	x	x
Quality of life questionnaires: EORTC QLQ C30, EORTC QLQ LC13	x		x		x	
CCI [REDACTED]					CC	
Lung function measurements spirometry: FEV ₁ , FVC, FEV ₁ /FVC ratio, and PEF	x	x			x	
Pulse oximetry – oxygen saturation	x	x			x	
Activity step count		x				
Training on Current Wearable Health Monitoring System	x					
Durvalumab treatment ^c	x			x	x	

AE = adverse event; EORTC QLQ C30 = European Organization for Research and Treatment of Cancer Quality of Life Core Questionnaire; EORTC QLQ LC13 = European Organization for Research and Treatment of Cancer Quality of Life Lung Cancer Module; FEV₁ = forced expiratory volume; FVC = forced vital capacity; NSCLC = non-small cell lung cancer; PEF = peak expiratory flow

^a Information regarding concomitant medication (including over-the-counter medications) will include, when available: drug name, indication for treatment, route, and duration of drug administration.

^b Adverse event collection (including event description, intensity/severity, outcome, action taken, etc.) will occur at Baseline (i.e., after the patient signs the ICF), during standard of care visits, at the End-of-Study visit, and for 30 days after the End-of-Study visit to capture late-onset symptoms.

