4.2.4.8 Adverse Events

An AE for drugs is the occurrence of an undesirable medical condition or the deterioration of a pre-existing medical condition following or during exposure to a pharmaceutical product or device, whether or not considered causally related to the product or device. An AE for medical devices is any untoward medical occurrence, unintended disease or injury, or any untoward clinical signs (including an abnormal laboratory finding) in patients, users, or other persons whether or not considered related to the medical device. This includes events considered related to the medical device and events considered related to the study procedures involved. AEs will be collected throughout the study, from informed consent until 30 days after the End-of-Study visit.

Treatment-emergent adverse events (TEAEs) are defined as any AEs that occur or worsen at any time after the start of administration of the first dose of durvalumab and through 30 days after the last dose of durvalumab. Treatment-emergent AEs will be characterized based on the onset date relative to each patient's first dose date. For adverse events with incomplete start dates, the imputed dates will be used to determine whether the adverse events are treatment emergent.

Adverse events will be summarized by the SOC and PT based on the MedDRA dictionary version 22.1 or later. The CTCAE grades will be summarized by SOC and PT, using the current version of National Cancer Institute (NCI) CTCAE. For summaries by SOC and PT, a patient will be counted once at the SOC level and once at each PT within the SOC level. For

summaries by SOC, PT, and CTCAE Grade, a patient will be counted once at the highest grade for which the event occurred at the SOC level and the highest grade for each unique PT within that SOC level. Therefore, patients may only contribute once to each PT and once to each SOC level. The summaries presenting frequency of AEs by SOC and PT will be ordered by overall descending frequency of SOC and then, within a SOC, by overall descending frequency of PT.

The following AE tables will be provided:

- TEAEs, overall and by SOC and PT
- TEAEs related to pneumonitis by maximum relationship, overall and by SOC and PT
- TEAEs related to medical devices by maximum relationship, overall SOC and PT

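### Protocol 8.2.1 says patients will be told the devices add no risk, which conflicts with the device events reported in Protocol 2.3 and with 8.2.1's own disclosure duty

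*Protocol*

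**What the plan says.** Protocol 8.2.1 (Patient Informed Consent) sets out what patients are to be told. It opens by requiring that they receive "full and adequate oral and written information about the nature, purpose, possible risk, and benefit of the study". Later in the same section it says it will be clearly explained to them that "the use of these devices will not involve any additional risk for the patient".

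Protocol 2.3 (Benefit/Risk Assessment) describes the same technology differently. Of the technology as a whole it says "it is believed to pose an extremely low risk to study patients". It then gives specifics: "Patients using the wearable arm device have reported minor events of skin irritation and discomfort during sleeping", and "patients undergoing concomitant anti-coagulation therapy have experienced ecchymosis near the device site". It adds that "study-related or multiparametric mobile technology-related AEs are expected to be rare".

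The rest of the plan treats device harm as possible. Table 1 in Protocol 7.3 has a row for "All AEs/SAEs (including durvalumab-related and device-related AEs", Protocol 8.3.1.2 defines adverse events and serious adverse events for medical devices, and SAP 4.2.4.8 lists a table of "TEAEs related to medical devices by maximum relationship, overall SOC and PT".

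**The concern.** The two sections cannot both be followed. A site cannot disclose the events in Protocol 2.3 and also tell the patient that the devices add no risk. What is at stake is the accuracy of consent. The devices are the reason the study is interventional, and patients agree to use them daily for up to 12 months (Protocol 5.1, criterion 5). A statement of no additional risk, if delivered as written, would be inaccurate for all 75 planned patients. It would matter most to those on anticoagulants, because the ecchymosis was reported in that group.

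**Working it through.** No arithmetic applies: neither document gives a rate for any device event, and the plan has no figure to reproduce. The check is a comparison of current text, taken step by step.

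1. **Level of risk.** Protocol 8.2.1 says none is added. Protocol 2.3 says extremely low, with related events expected to be rare. Low and rare are not the same as none.

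2. **Specific events.** Protocol 2.3 names three: skin irritation and discomfort in sleep among users of the arm device, both called minor, and ecchymosis close to the device in patients on anticoagulants. Protocol 8.2.1 names none of them.

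3. **Could the word additional reconcile the two?** It could if it meant risk beyond what the patient would face without joining, and the devices were part of routine care. They are not. Protocol 2.3 describes all the other procedures as standard of care, Protocol 6.2 makes the mobile technology the primary exposure, and Protocol 8.3.2 calls the devices the study intervention. Any risk from the devices is therefore the risk added by taking part.

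4. **Can the events occur in enrolled patients?** Yes. All patients wear the device. Protocol 5.2 contains no exclusion for anticoagulant use, so the group in which ecchymosis was reported can enroll. How many such patients to expect is not stated.

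5. **Consistency within 8.2.1.** The section's own opening requires full and adequate information on possible risk. Meeting that requirement means conveying what Protocol 2.3 reports, which contradicts the later clause. The section is therefore internally mixed.

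6. **A possible origin.** The version history records that Amendment 2 added the wearable risk description to Protocol 2.3, and its list of changes names no matching edit to 8.2.1. That would explain the mismatch, but the conclusion does not depend on it, because both statements stand in the current text.

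**The case against.** The strongest reply is that one loosely worded clause does not determine what patients learn. They are informed by the consent form and the discussion around it. Protocol 8.2.1 itself demands full risk information and consent that meets 21 CFR 50. Protocol 8.2 requires IRB approval of the final protocol together with the final consent form, so the board sees the benefit/risk section beside the consent text. The events are minor or local, and the practical distance between extremely low and no additional risk is small.

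Much of this stands. These safeguards make it quite possible that the consent form is already correct, and they keep the point modest. They do not make the clause true. It prescribes what is to be explained, and an explanation that followed it would be wrong whatever the form says.

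Three stronger readings are tempting and are not supported:

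- A reader might infer that patients are being misinformed. The consent form was not available for review, so this is conditional on sites following the clause literally.
- A reader might infer that the device is known to cause these events. Protocol 2.3 says that users reported or experienced them. It suggests a link but does not assert causation, and it describes the irritation and discomfort as minor.
- A reader might infer that reassured patients will under-report skin events, so that the device-related table comes out too low. Nothing in the documents shows this, and the collection plan points the other way. Adverse events are collected at baseline, at standard of care visits, at the End-of-Study visit and for 30 days afterwards (Protocol 8.3.1.3). They are recorded by the study physician regardless of causality (Protocol 8.3.1.4), and device-related events are named explicitly in Table 1.

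**Conclusion.** The clause in Protocol 8.2.1 is wrong as written. It is inconsistent with Protocol 2.3 and with the disclosure duty in its own section. This is an internal inconsistency about what patients are told, not a flaw in the design or analysis: no endpoint, sample size, analysis set or estimate changes, and no effect on the device-related adverse event table is claimed.

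The clause covers all 75 planned patients. The ecchymosis finding bears only on those taking anticoagulants, whose number is not given. The size of the risk cannot be stated from the documents. The conclusion assumes only that Protocol 2.3 is a correct account of what has been reported with the wearable. Whether any patient receives an inaccurate statement depends on the unseen consent form and on how sites conduct the discussion. The change is worth making because the clause concerns disclosure of risk from the study intervention, but the low grade of the reported events means it is not a blocking defect.

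**What to change.** Reconcile Protocol 8.2.1 with Protocol 2.3. Remove the no-additional-risk clause and put in its place the content that 2.3 already contains: the risk is believed to be extremely low; minor skin irritation and discomfort in sleep have been reported by users of the wearable; and ecchymosis close to the device has been reported in patients on anticoagulants. Then check the consent form, and any site script for the consent discussion, against that wording.

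The cost is one sentence in the protocol and one document check. If the form already lists these events, only the protocol sentence needs to change. If it repeats the clause, the form needs the same correction and IRB approval of the revised text. No eligibility rule, procedure or analysis is affected.

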8.2.2 Confidentiality of Study/Patient Data

The patient's ICF will incorporate wording that complies with relevant data protection and privacy legislation. Pursuant to this wording, patients will authorize the collection, use, and disclosure of their personal data by the physician to those persons who need that information for the purposes of the study.

The ICF will explain that study data will be stored in a web-based platform, maintaining confidentiality in accordance with local laws for data protection.

The ICF will also explain that for quality check purposes, a monitor from Syneos Health will require direct access to the signed ICFs. In case source data verification is planned as a quality check, the ICF will explain that for data verification purposes, a monitor from Syneos Health may require direct access to source documents relevant to the study.

8.3 Management and Reporting of Adverse Events and Device Complaints

8.3.1 Management and Reporting of Adverse Events

The focus of this study is to assess whether multiparametric mobile technology allows earlier detection and intervention of pneumonitis and other pulmonary events in the patient population.

8.3.1.1 Definition of Adverse Event and Serious Adverse Event for Drugs

An AE is the occurrence of an undesirable medical condition or the deterioration of a pre-existing medical condition following or during exposure to a pharmaceutical product or device, whether or not considered causally related to the product or device. An undesirable medical condition can be symptoms (e.g., nausea, chest pain), signs (e.g., tachycardia, enlarged liver), or the abnormal results of an investigation (e.g., laboratory findings,

electrocardiogram). In clinical studies, an AE can include an undesirable medical condition occurring at any time after the Baseline visit (Day 1) once the patient signs the ICF, even if no study treatment has been administered. A treatment-emergent AE (TEAE) is an AE that starts or worsens at any time after initiation of a pharmaceutical product on the first day of treatment through the End-of-Study visit.

An SAE is an AE occurring during any study phase after the patient signs the ICF (i.e., at Baseline, treatment, washout, follow-up) that fulfills 1 or more of the following criteria:

- Results in death
- Is immediately life-threatening
- Requires in-patient hospitalization or prolongation of existing hospitalization
- Results in persistent or significant disability/incapacity or substantial disruption of the ability to conduct normal life functions
- Is a congenital abnormality or birth defect
- Is an important medical event that may jeopardize the patient or may require medical intervention to prevent 1 of the outcomes listed above

Adverse Events (AEs) for malignant tumors reported during a study should generally be assessed as SAEs. If no other seriousness criteria apply, the “Important Medical Event” criterion should be used. In certain situations, however, medical judgement on an individual event basis should be applied to clarify that the malignant tumor event should be assessed and reported as a non-serious AE. For example, if the tumor is included as medical history and progression occurs during the study, the AE may not fulfil the attributes for being assessed as serious, although reporting of the progression of the malignant tumor as an AE is valid and should occur.

Life-threatening in this context refers to a reaction in which the patient was at risk of death at the time of the reaction; it does not refer to a reaction that hypothetically might have caused death if more severe.

Medical and scientific judgement should be exercised in deciding whether other situations should be considered serious reactions, such as important medical events that might not be immediately life-threatening or result in death or hospitalization but might jeopardize the patient or might require intervention to prevent one of the other outcomes listed above.

